### **Purpose**

The purpose of the research is to study a new safety monitoring system developed by SafelyYou to help care for a loved one with dementia. The goal is to provide better support for unwitnessed falls.

The SafelyYou Guardian system is based on AI-enabled cameras which detect fall related events and upload video only when these events are detected. The addition of a Human in the Loop (HIL) will alert the facility staff when an event is detected by the system. This would allow the facility to continue with its current safety precaution but add another level of support by using HIL's to monitor for falls in real-time and 24/7.

This process enables staff to know about falls without requiring residents wear a device and to see how falls occur for residents that cannot advocate for themselves while still protecting

Revision Date: 10/23/19

resident privacy by only uploading video when safety critical events are detected. Seeing how the resident went to the ground (1) prevents the need for emergency room visits when residents intentionally moved to the ground without risk and (2) allows the care team to determine what caused an event like a fall and what changes can be made to reduce risk.

## **AIMS & HYPOTHESES FOR RANDOMIZED, WAITLIST-CONTROL STUDY.**

**Aim #1. To assess whether SafelyYou Guardian + HIL will lower fall rates.** Hypothesis 1. Compared to standard-of-care (waitlist control group), SafelyYou Guardian will reduce fall rates in study participant over the study period of 6 months.

**Aim #2. To assess how use of the SafelyYou Guardian affects time spent on the ground after a fall.** Longer time to fall discovery is associated with higher human suffering and often leads to higher medical morbidity/mortality. Hypothesis 2: SafelyYou Guardian + HIL will reduce time to fall discovery (time from fall to staff notification) to under 5 minutes and reduce time spent on the ground to under 15 minutes. Since there is no way to measure control participants time spend on the ground, the aim will not have a comparison but will be descriptive.

**Aim #3. To assess whether SafelyYou Guardian will lead to improvement in hard clinical outcomes.** Hypothesis 3: SafelyYou Guardian participants will lower ED visits and hospitalizations when compared to control. This reduction in ED and hospitalization will correlate with reduced fall rates (aim #1) and reduced time spent on the ground (aim #2). We will review the strength of the association with aim #1 and #2 outcomes.

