For aim #3, we will ascertain the occurrence of fall in the intervention group by doing follow-up case review of each detected fall. For the control group, we perform biweekly check with facility staff and family regarding knowledge and documentation of any falls. For falls in both the intervention and control group, we will additional collected data regarding occurrence of ED visit and hospitalization days. We will also include occurrence (or absence) of any operations, intensive care unit stays, and other medical procedures. We will also collect mortality data.

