**Privacy and security safeguards.** Privacy: A common concern with any video-based monitoring system is privacy. Through the series of pilots discussed previously and shown in Fig. 3, we have systematically validated the privacy/safety tradeoffs for residents, families, staff, owners, and operators of memory care facilities. Pilot 2 demonstrated at small scale (one facility, 10 residents) that the industry would be receptive to video-based fall detection and prevention. Pilots 3 and 4 confirmed the approach with 11 facilities and 87 residents while demonstrating significant positive outcomes including 37% reduction in use of EMS for falls and 38% reduction in total falls. We now have paid commitments for 480 beds and ongoing discussions regarding expansion within the networks from the Phase I facilities, validating the benefits outweigh potential privacy and legal concerns for a number of families and providers. The combined benefits of (1) reduced time on the ground due to real-time intervention of front line staff, (2) immediate assessment of severity when a resident is found on the ground without witness, and (3) reduced likelihood of future falls through intervention of OT make our commercial approach viable. The key point is that as dementia progresses, the need to keep a loved one safe often surpasses concerns regarding their privacy. The benefits provided by SafelyYou in terms of reduced falls and ED visits have surpassed the concerns for the majority in memory care facilities where 85%-90% opt-in for the system. For more information from families and care staff validating these numbers and sentiments, please see letters from [name], [name], [name], [name], and video:

<https://youtu.be/ThUsBVOAJ3A>. This video was made with explicit permission from all residents/families for the purposes of promoting our work and supporting further recruitment. During pilots 2, 3 and 4, no live video was available and video was recorded whenever motion was detected. For new customers signing up for the system and for the Phase II clinical trial, no live video access is available and videos that do not contain a detected fall are not kept after 60 seconds as enabled by the highly accurate fall detection system developed in Phase I. We have never placed video cameras in bathrooms and will not for the Phase II clinical trial. In our 11 partner facilities, the Phase I showed that only 5-10% of

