#### **Data collection:**

Demographic and clinical data set: We collect demographic data including age, gender, race/ethnicity, primary clinical diagnoses for SNF stay with specific focus on dementia subtype, most recent orthopedic surgery (<3 months) or reason for hospitalization, chronic medical conditions (top 3), and baseline medications (number of medications). Beyond the data collected from the video, data specific to the falls is collected either by direct extraction from the platform or from incident reports kept by facilities as (State regulations require facility track and file incident reports for all known falls). For the control population, the time of unwitnessed falls is unknown, but the number of falls and ER visits is collected from the existing facility incident reports. For the population equipped with SafelyYou Guardian, we will have direct access to the time of the fall, the time it took the HIL to verify the fall and call the facility, and the time on the ground. Note that for the residents with SafelyYou Guardian, we expect these values to be in increments of minutes.

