#### Clinical outcomes.

For Aim #1, the primary outcomes are the number of falls detected by facilities using the adverse incident reporting system as per routine facility protocol. While use of video detected falls will be used in the intervention group to assist with prevention of future falls, we will not use this as the actual outcome measure: is not the standard-of-care, and the control group will not have video recorded outcomes. There is a bias for detecting falls using video since existing fall reporting systems do not capture falls which staff do not know about (e.g., when a resident is able to get back in bed after a fall). Staff-detected falls which automatically trigger adverse incident reporting is the “real-world” outcome measure and current stand-of-care. Thus, outcomes will differ by facility (each facility has different adverse incident reporting operations and implementation, hence the randomization at each facility will adjust for such variables).

Aim #2 will be a naturalistic observation of SafelyYou Guardian with HIL for 6 months. Specifically, for all the facilities, the use of the SafelyYou Guardian enables direct notification of falls to front-line staff in the facilities, by intervention of the HIL. We can directly measure time on the ground for the residents as follows: (1) The time of the fall is recorded by

SafelyYou Guardian (which detected it); (2) The time of intervention of the front-line staff is logged by the staff after finding the residents on the ground. This means that for the population with treatment, we can directly measure the time of fall discovery (successful call leading to front line staff intervention), and time on the ground (since time of the intervention is logged by the facility). This is because time on the ground for monitored residents can be measured precisely by video recording. Reduction of the time on the ground can be computed given the difference between the two.

Aim #3 will include number of ER visits and number of hospitalizations. We will obtain information about resident demographics, medical comorbidities, emergency room visits, and hospitalization data by asking the study participant legal representatives. In addition, we will have participant / participant Durable Power of Attorney complete HIPAA consent forms for release of medical records when indicated if the details of data are not available.

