Following the sample size for a time-averaged response methodology laid out in Fitzmaurice et al., we adjusted the total number of centers needed by a factor related to the number of observed months, anticipated participants per center (30% of 35 participants per center with 10% dropout) and the correlation between measurement months. The dropout rate was roughly at ~1% per month so a 10% dropout over 6 months is a conservative estimate. We assumed an extremely conservative estimate of the correlation between time points (months) of 0.8 and 6 months of follow-up. Reproducible R code is available at <https://github.com/[name]/>. We estimate that a total sample size of 460 ( $n=230/\text{arm}$ ) out of 19 facilities will be needed for a power of 80% to detect a 30% reduction in falls in the intervention group vs. control. Our approach of focusing on estimation and uncertainty and accepting the sample size collected for the main study, is congruent with experts' recommendations stating that the purpose of economic evaluation is not hypothesis testing; given there is no hypothesis testing, there is no requirement for a separate sample size calculation. For Aim 2, we will use similar descriptive statistics as described in Aim 1. For Aim 3, We will use a multivariate regression model to examine predictors of the main outcome, ER visits and hospitalizations (binary variable), using time to fall discovery by staff and time spent on the ground as the main predictors while controlling for baseline participant characteristics and facility characteristics.

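### Hypothesis 3 counts a correlation of ED visits and hospitalizations with fall rates as part of what is to be shown, but a positive correlation is expected even with no intervention effect

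*Combined protocol and SAP*

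**What the plan says.** Under Aims & Hypotheses, Hypothesis 3 has two parts. The first is a randomized contrast: "SafelyYou Guardian participants will lower ED visits and hospitalizations when compared to control". The second is a prediction about association: "This reduction in ED and hospitalization will correlate with reduced fall rates (aim #1) and reduced time spent on the ground (aim #2". The section closes with "We will review the strength of the association with aim #1 and #2 outcomes". It gives no unit of analysis, reference value or decision rule for that association.

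Three places describe where the ED and hospitalization data come from:

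- Design, Aim 3 paragraph: "For falls in both the intervention and control group, we will additional collected data regarding occurrence of ED visit and hospitalization days".
- Data collection, for controls: "the number of falls and ER visits is collected from the existing facility incident reports".
- Clinical outcomes, Aim 3 paragraph, where the plan obtains "emergency room visits, and hospitalization data by asking the study participant legal representatives", with no restriction to falls.

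The only Aim 3 model, in the Data analysis paragraph, takes as its outcome "ER visits and hospitalizations (binary variable), using time to fall discovery by staff and time spent on the ground as the main predictors". Fall count is not named as a predictor.

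**The concern.** If an ED visit is recorded because a fall was recorded, the ED count is largely a subset of the fall count. The two then move together in any population of fallers, treated or not. A positive association is what an inert intervention would also produce, yet the wording of Hypothesis 3 invites the reader to take it as corroboration.

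The protocol claims two routes to fewer ED visits: fewer falls, and fewer transfers per event because staff can see how the resident reached the ground. A correlation with fall counts cannot tell these routes apart, and it cannot tell either of them from no effect. At stake is how Aim 3 is interpreted, not the validity of its randomized comparison.

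**Working it through.** **Inputs from the documents (Data analysis paragraph).** Monthly fall rate 0.49; between-facility variation in log fall rate 0.467, taken as a standard deviation; 460 residents in 19 facilities; 1:1 allocation within facility; 6 months; between-month correlation 0.8; 30% target reduction.

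**Assumptions, not in the documents.** Probability p that a fall leads to an ED visit: 0.1, 0.3 or 0.5. Resident frailty: none, or gamma with variance 1. Non-fall ED visits: none, or 0.1 per resident-month. Significance level: 5% two-sided.

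**The plan's own figure.** The documents give no figure for this correlation. The fall inputs can be checked against the Aim 1 sample size:

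- Marginal rate: 0.49 × exp(0.467²/2) = 0.546 per month.
- One-month n per arm: (1.960 + 0.842)² × (1/0.546 + 1/(0.7 × 0.546)) / (ln 0.7)² = 274.2.
- Time-averaging factor: (1 + 5 × 0.8)/6 = 0.833.
- n per arm: 274.2 × 0.833 = 228.5, so 458 in total against the stated 460.

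The match holds without inflation for dropout, which is a separate matter.

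**Closed form at zero effect.** Let falls F be Poisson with mean μ, and ED visits given F be Binomial(F, p). Then Cov = pμ, Var(F) = μ and Var(ED) = pμ, so the correlation is √p: 0.32, 0.55 and 0.71 at p = 0.1, 0.3 and 0.5. If residents' rates vary with squared coefficient of variation c, the correlation is √[p(1 + cμ)/(1 + pcμ)]. With μ = 0.49 × 6 = 2.94 and c = 1 this is 0.55, 0.79 and 0.89. With 460 residents, a correlation above about 1.96/√460 = 0.09 is significant.

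**Simulation at zero effect.** 400 trials per setting, with facility variation included. Resident level is the Spearman correlation of fall and ED counts. Facility level is the correlation, over 19 facilities, of the control-minus-intervention difference in mean ED visits with the same difference in falls; in brackets is the share of trials significantly positive, which would be about 2.5% if there were no association.

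| Frailty | Non-fall visits per month | Resident level, p = 0.1 / 0.3 / 0.5 | Facility level, p = 0.1 / 0.3 / 0.5 |
|---|---|---|---|
| none | 0 | 0.37 / 0.62 / 0.77 | 0.30 (28%) / 0.54 (74%) / 0.69 (92%) |
| none | 0.1 | 0.22 / 0.49 / 0.67 | 0.19 (14%) / 0.41 (43%) / 0.58 (79%) |
| variance 1 | 0 | 0.53 / 0.77 / 0.88 | 0.56 (76%) / 0.81 (99.5%) / 0.90 (100%) |
| variance 1 | 0.1 | 0.31 / 0.61 / 0.77 | 0.37 (40%) / 0.72 (96%) / 0.85 (100%) |

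The resident-level correlation was significantly positive in 99–100% of trials in every row. In the same null trials a between-arm test of ED visits (a t-test on the 19 facility differences) rejected in 3–7%, and a test for trend in ED visits per fall against fall count rejected in 3–8%, against a nominal 5%.

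**Does the correlation separate benefit from no benefit?** At p = 0.3 with fall-related visits only:

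| Quantity | True 30% fall reduction | No effect |
|---|---|---|
| Resident-level correlation, no frailty | 0.61 | 0.62 |
| Resident-level correlation, frailty | 0.75 | 0.77 |
| Facility-level correlation, no frailty | 0.61 (82% significant) | 0.54 (74%) |
| Facility-level correlation, frailty | 0.82 (99.8%) | 0.81 (99.5%) |
| Between-arm ED test rejects, no frailty | 88.5% | 5.0% |
| Between-arm ED test rejects, frailty | 61.5% | 4.5% |

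The between-arm test separates the two states of the world; the correlation hardly does.

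**The case against.** A reader might infer that the correlation is guaranteed: that a resident without a fall has no ED visit by construction, so that the fall-rate clause would be confirmed whatever the truth. The documents do not support that, for three reasons.

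- The Clinical outcomes section also obtains ER visits and hospitalizations from legal representatives and does not limit them to falls. Whether the outcome is fall-related or all-cause is unclear. Non-fall visits weaken the association, for example from 0.37 to 0.22 at p = 0.1 without frailty, but did not remove it in any setting tried.
- The sentence speaks of reductions, and a single resident in a parallel-group comparison has no individual reduction. On the facility-level reading the association is positive on average under no effect, but significant in anything from 14% to 100% of trials.
- No test, threshold or model is attached to the clause. The plan only says that the strength of association will be reviewed, and the specified model uses the time variables. That a trial report would claim confirmation is an inference.

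A reader might also take the pilot's "37% reduction in use of EMS for falls and 38% reduction in total falls" as showing that EMS use per fall did not change, since (1 − 0.37)/(1 − 0.38) = 1.016. The figures carry no intervals, the Design section says that earlier work used a baseline as control, and EMS use is not ED visits. They illustrate why the two factors should be shown separately and prove nothing more.

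Nor would this correlation credit faster response. That enters through the time variables, where the difficulty is a different one: controls have no time-on-ground measurement.

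These objections limit the wording. They do not remove the point: on every reading tried, an intervention with no effect still yields a positive association on average.

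**Conclusion.** The concern holds in this form: the association of ED visits and hospitalizations with fall rates cannot count as support for the intervention, because it is expected to be positive with no effect. At resident level it is about 0.3–0.9 if ED visits are fall-related and about 0.2–0.8 with non-fall visits at 0.1 per month, and significant in nearly all null trials. At facility level the mean is 0.19–0.90, significant in 14–100% of null trials. These sizes rest on the assumed ED probability per fall, frailty variance and non-fall visit rate; the direction does not depend on their exact values within the ranges tried. The simulations concern ED visits; hospitalizations collected for falls follow the same reasoning but were not simulated.

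The randomized comparison in the first sentence of Hypothesis 3 is unaffected, and the time-on-ground clause is a separate issue. Because the repair is specific and cheap, it should be made.

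**What to change.** 1. In Aims & Hypotheses, rest Hypothesis 3 on the between-arm comparison of ED visits and hospitalizations. Remove the fall-rate correlation as a criterion of support, or keep it and label it descriptive.
2. State whether ED visits and hospitalizations are fall-related or all-cause, and reconcile the Aim 3 paragraphs of Design and Clinical outcomes accordingly.
3. Report by arm, with 95% confidence intervals, falls per resident-month and fall-related ED visits per reported fall. Label the second descriptive: falls arise after randomization, and Design ascertains them differently by arm (case review of detected falls in the intervention group, biweekly checks with staff and family in controls).

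The cost is a few changed sentences, one small table from data already planned, and the loss of a supporting result that carries almost no information about whether the intervention works. If the outcome is declared all-cause, fall-related visits must still be flagged so that the per-fall figure can be computed.

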### Design

For Aim 1, we plan to recruit 460 study participants from 19 memory care facilities. For the purpose of this study, facilities will include Skilled Nursing Facilities (SNFs), or equivalent. Aim 1 will be a randomized controlled study using a waitlist control group. The randomization will occur at the individual (resident) level within each facility to control for variations at each facility in terms of facility size, facility administration, and staff training. During the first 6 months, n=230 will receive the intervention (SafelyYou Guardian, i.e. real-time alarms through a phone call from the HIL to the facility, front line staff intervention, and OT review), and n=230 will not receive the intervention. This design is the most rigorous way to test the intervention against the control: the randomization allows for control of confounding variables and has been previously used in the evaluation of medications, non-pharmacological, and mobile electronic interventions (where use of placebo treatment and blinding is not feasible) [87-89]. Previous work used a baseline as control, allowing possible confounding variables. As we recognize that 50% of the interested participants will not receive the intervention, those residents will be offered the intervention for a 6-month extension period (in order to accomplish Aim 2). This is the best compromise between the need for a rigorous randomized controlled trial vs. ethical responsibility to maximize benefit to each study participant.

For Aim #2, we will measure response times to each fall and the amount of time a resident spends on the ground after each fall. We intend to include all 460 participants' data from Aim #1. These will be participants who receive the initial intervention (n=230) and the additional participants who are on the waitlist control group who will receive the intervention in the second 6month period. The design for Aim #2 is observational in nature. The significance is that a large cohort of video data about the naturalistic progression of falls in residents with dementia has never been conducted to our knowledge. We will determine if the two time variables (time to fall discovery by staff and time spent on the ground after a fall, controlling

for baseline participant characteristics – i.e., demographics and medical conditions) and facility size, will predict need for ER visits or hospitalizations.

For aim #3, we will ascertain the occurrence of fall in the intervention group by doing follow-up case review of each detected fall. For the control group, we perform biweekly check with facility staff and family regarding knowledge and documentation of any falls. For falls in both the intervention and control group, we will additional collected data regarding occurrence of ED visit and hospitalization days. We will also include occurrence (or absence) of any operations, intensive care unit stays, and other medical procedures. We will also collect mortality data.

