#### Participant recruitment and retention

In the Phase I project, recruitment was performed by hosting a family night with care staff from the facility. Recruitment rate among families attending family nights was 85%. Our retention over 10 months with the 11 partner facility was near 100% (no family / resident ever requested to remove the system). One resident did begin taking the sign off the door after enrolling in the study, and the system was removed with approval from the family since he may have been attempting to object to the study. We credit this high retention to the very little burden required.

The recruitment of 460 residents will happen in batches (we expect to have access to our entire cohort 6 months from the start of the project). Once the resident population is recruited, we will deploy the system and onboard the facility staff. Onboarding will be gradual over 3 months. Through randomization, the population is split in half. One half, the control group, will not receive the intervention for the first 6 months, but will get the intervention for the next 6 months. The other half, the intervention group, will be in the study for the first 6 months only and then continue for the next 6 months. In total, 12 months will be needed per cohort. Installing the system requires 1-5 days depending on the facility size to mount the SafelyYou Guardian in the electrical closet alongside the router and PoE switches required to connect and power the cameras. Installation will be provided by SafelyYou contractor.

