### **Study procedures**

After informed consent, each participant will be randomized to either standard-of-care (wait list control) vs. intervention. We will randomize participants within each facility as they are enrolled into the study. This ensures that site differences such as size, staff training, and other confounding variables will be controlled for by having a balanced number of intervention/control participants per site. Family meetings and staff education sessions will be conducted at each site.

If Legally Authorized Representatives wish to access recorded fall videos at any time, they can do so by contacting facility staff so they can walk through recorded video for the resident at the facility. These are sensitive videos, so we require Legally Authorized Representatives to visit the facility to view the videos with facility staff.

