Event Detection: As videos are recorded at the facility, the computer located in the facility will analyze the video streams and keep a buffer of 10 minutes of prior video from each camera. If a resident is detected on the ground or a resident is detected going from a laying position to a sitting position in bed, an alert will automatically be sent to the Magellan team, and the 10-minute buffer video will be uploaded. They will confirm a resident is on the ground by viewing a blurred version of the video as described above and reach out to the facility staff by phone or e-call system to inform them of the situation. The 10 minutes of video after a resident on the ground is confirmed will also be uploaded, enabling 20-minute window into how the fall occurred with minimal burden on the frontline care team. As long as an event such as a resident on the ground is detected, the system will continue to upload video in this way.

Abuse Reporting: Abuse reporting will be conducted following the requirements of the Welfare and Institutions (WIC) code. If any potential evidence of abuse is discovered, facility management will be immediately alerted. Note that evidence of abuse may be missed by the SafelyYou system since only video of detected events is uploaded. The SafelyYou system is not meant to be a system for reporting abuse; it is meant to be a system for improving fall prevention practices in memory care. The research system is not intended to screen for abuse or theft suspicions. As discussed below, only video of detected events are available. It is thus very possible that incidents of abuse or theft are never uploaded for viewing by facility personnel.

Confidentiality: Study data will be handled as confidentially as possible. If results of this study are published or presented, individual names and other personally identifiable

information will not be used unless you give explicit permission for this in the separate media release form.

To minimize the risks to confidentiality, we will do the following:

- During data collection, all data will be transmitted over a secure channel.
- Research records, including video recordings and computer-based data, will be stored in an encrypted format, on a password-protected computer in a physically secure room.

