## **Risk/Benefit Assessment**

Minimal risk for study participants is expected as the system does not physically interact with study participants in any way and only provides supplementary support while all existing safety protocols in the facility remain in place.

Risks and/or discomforts include loss of privacy by placing a camera in the private room. Although the system is designed to keep video only when a fall is detected, false alarms do occur which can cause video to be uploaded at any time. If subjects feel uncomfortable about privacy once the cameras are installed, they may withdraw from the study at any time.

The research study personnel take several steps to protect the privacy of each participant. The recorded video does not have audio capability in order to protect private communication of residents and their visitors. Physical signs are posted visibly at the entrance to all private rooms containing cameras. The signs state that video recording is in progress to ensure all visitors and staff entering the room are aware of the camera. Cameras are placed in the private bedroom only, not in the private bathroom. Cameras record video only when an event is detected. Video (with no audio) will be reviewed by the research study personnel after collection. If more than one resident occupies a room, all roommates must provide informed consent for any to participate. All data is encrypted in transit and at rest.

Installation of the wall-mounted cameras will require inserting screws into the wall in the corner of the room adjacent to the ceiling and installing cabling which may be visible. No other risk of property damage is expected.

The ongoing safety procedures at the facility will remain in place.

The SafelyYou system has demonstrated reduced fall risk and unnecessary emergency room visits for those using it in previous studies with under 100 residents enrolled and hundreds more that have used it as a commercial product. We believe the system will provide significant benefits through faster response times to safety-critical situations, help staff make informed decisions about the need for transfer to the emergency room following unwitnessed falls, and reduce the overall frequency of falls through improved root cause analysis to minimize the risk of repeat falls, but this is active research, and we do not know if any of these benefits will occur for certain.

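### Residents are randomised individually and no rule covers shared rooms, so enrolled roommates can land in different arms and a control may be exposed to the camera

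*Combined protocol and SAP*

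**What the plan says.** Under Design, "The randomization will occur at the individual (resident) level within each facility". Study procedures adds the timing: "We will randomize participants within each facility as they are enrolled into the study". Facility is the only grouping mentioned for allocation.

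The Risk/Benefit Assessment allows for shared rooms: "If more than one resident occupies a room, all roommates must provide informed consent for any to participate". It also places the device: "Cameras are placed in the private bedroom only, not in the private bathroom", wall-mounted in a corner near the ceiling.

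The Event Detection paragraph of Study procedures sets the trigger. It begins "If a resident is detected on the ground" and adds sitting up in bed as a second trigger. An alert is then sent, video is uploaded and the facility is contacted. The Recording paragraph makes event video available to facility staff.

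Design defines the intervention as three components: real-time phone alarms, front-line staff response and OT review. Participant recruitment and retention says of the waitlist half that "the control group, will not receive the intervention for the first 6 months".

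The Poisson mixed model under Data analysis accounts for nesting within centres. It has no term for rooms.

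**The concern.** Nothing in the plan gives roommates the same arm, makes the room the unit of allocation, or limits randomisation to one resident per room. When both occupants of a room are enrolled and randomised, one can be allocated the camera and the other not. Neither the trigger nor the verification step is described as distinguishing the intervention resident from a control in the same bedroom.

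Such a control could receive two of the three components (alarms and staff response), and staff could see the event video. That is not the standard-of-care comparator that Design and the recruitment section describe.

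Two comparisons are affected:

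- **Aim 3.** The Purpose section says that seeing how a resident reached the ground avoids emergency visits when the move was intentional and without risk. Exposure could therefore change a control's ED use.
- **Aim 1.** The Purpose section also says that video lets the care team find causes and reduce risk, which could lower falls in exposed controls and dilute a true effect. But the outcome is falls that staff know about, so alerts could raise the exposed control's reported count and exaggerate the effect.

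The two Aim 1 mechanisms pull in opposite directions.

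**Working it through.** **Inputs from the document.** 230 per arm, 80% power, 30% reduction, within-person correlation 0.8 and 6 months of follow-up with 10% dropout (Data analysis). Monthly fall rate 0.49 and between-centre variation in log rate 0.467, read as a standard deviation (same section). Allocation is 1:1.

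**Assumed, because not stated.** Two-sided alpha 0.05; the share s of participants whose roommate is also randomised; the proportional reduction e in falls that an exposed control receives; and the within-room correlation (ICC).

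**Step 1: the plan's own figure.** The plan used simulation followed by an adjustment for repeated months. A closed formula comes close.

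- Marginal control rate: 0.49 × exp(0.467²/2) = 0.546. Intervention rate: 0.70 × 0.546 = 0.383.
- Repeated-months factor: (1 + 5 × 0.8)/6 = 0.833.
- n per arm = (1.960 + 0.842)² × (1/0.546 + 1/0.383) / (ln 0.70)² × 0.833 = 228.5, against 230 stated.
- Power at 230 per arm: standard error 0.1269; 0.3567/0.1269 − 1.960 = 0.851; power 80.3%.

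This match is not unique. It leaves out dropout: with 207 per arm (230 × 0.90) power is 76.0%. Using 0.49 directly requires 254.8 per arm, and gives 75.9% power at 230. The formula serves only to show relative changes.

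**Step 2: how many pairs split.** Independent 1:1 allocation splits half of the pairs. With exact balance among 24 residents in a facility the figure is 12/23 = 52%. About s/2 of controls would share with an intervention resident: 230 × s/2 = 0, 6, 12, 23 and 46 at s = 0, 5, 10, 20 and 40%.

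**Step 3: dilution only.** Set the control rate to rc = 0.546 × (1 − e × s/2) and ri = 0.383. Then power = Φ(|ln(ri/rc)| / √[0.833 × (1/(230 rc) + 1/(230 ri))] − 1.960).

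Example with e = 0.15 (half the effect) and s = 20%: rc = 0.538, rate ratio 0.711, standard error 0.1273, and 0.3416/0.1273 − 1.960 = 0.723, so power is 76.5%.

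| s | Power, e = 0.15 | Power, e = 0.05 |
|---|---|---|
| 0% | 80.3% | 80.3% |
| 5% | 79.4% | 80.0% |
| 10% | 78.4% | 79.7% |
| 20% | 76.5% | 79.1% |
| 40% | 72.4% | 77.8% |

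**Step 4: what s might be.** Suppose a share d of residents live in double rooms, roommates consent independently with probability c, and consent means enrolment (all assumed). A room with one refusal is excluded, so s = dc²/(dc² + (1 − d)c).

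- With c = 30% (Data analysis) and d = 10, 20 and 40%, s = 3, 7 and 17%.
- The planned total implies a higher c: 460/19 = 24.2 per facility, and 24.2/35 = 69%. Then s = 7, 15 and 32%.

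Since d is unknown, neither set is an estimate. No figure is possible for Aim 3, because the document gives no ED or hospitalisation rates.

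**The case against.** The strongest reply is that the harm depends on four things the document does not establish: that rooms are shared, that both occupants are randomised and not merely consented to filming, that the camera sees both beds, and that calls are made for the control's falls. Most of the wording is about private rooms, and field of view is not stated. All of this stands. The number of exposed controls may be near zero, and coverage of the roommate is an inference.

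A reader might go further in several ways that the document does not support:

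- **A large loss of power.** Giving exposed controls the full 30% effect at s = 40% brings power to 63.1%. But Design includes OT review in the intervention, the Privacy paragraph credits OT with reducing future falls, and no passage gives OT review to such a control.
- **A breach of the outcome rule.** Clinical outcomes says "the control group will not have video recorded outcomes". That phrase explains why incident reports, and not video, are the Aim 1 measure in both arms. Footage of a control would not break it.
- **A conservative bias.** Alerts could raise reported falls among controls, so bias toward no difference cannot be assumed.
- **No remedy afterwards except exclusion.** An analysis as randomised, with a sensitivity analysis for exposed controls, would remain available.

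It is also fair to say that the uncertainty in base power (80.3% or about 76%) exceeds most of the differences in the table, and that the fix does not always gain power. At s = 40%, no change with e = 0.05 gives 77.8%, while room allocation with ICC 0.2 gives 77.2%. The case for the change is therefore a clean comparator more than power.

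**Conclusion.** The concern holds as a gap in the allocation rule. Followed as written, the plan can place enrolled roommates in opposite arms and expose the control to components that Design and the recruitment section withhold for 6 months. It does not show that this will happen often, or in which direction it would bias the result.

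Under dilution alone, the loss is at most about 4 power points for s up to 20% and about 8 points at 40% if exposed controls get half the effect. It is at most about 2.5 points if they get a 5% reduction. These figures rest on the assumed formula, alpha, s and e, and on a base that omits dropout. The sponsor can count shared rooms, so the point is easy to settle before randomisation.

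**What to change.** Randomise by room within facility:

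- All enrolled occupants of a room at the time of randomisation share one allocation, made only after all of them have consented. Single rooms are unchanged.
- A resident who joins an already allocated room in the first 6 months is not randomised into the between-arm comparison, because the arm would be known before consent.
- Use room-clustered standard errors for falls, ED visits and hospitalisations.
- Record room sharing at baseline and room moves, analyse by original allocation, and add a sensitivity analysis for controls exposed through moves.
- State the number of shared rooms.

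**Cost.** The variance rises by about 1 + s × ICC. At s = 5, 10, 20 and 40%, power is 80.1, 79.9, 79.5 and 78.7% with ICC 0.1, and 79.9, 79.5, 78.7 and 77.2% with ICC 0.2 (both ICCs assumed, base 80.3%). Balance within a site can be slightly looser when a room holds two. A few late joiners are lost to the comparison, but the recruitment section limits this: "Once the resident population is recruited, we will deploy the system and onboard the facility staff".

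Keeping individual allocation and excluding both occupants of split rooms leaves 230 × (1 − s/2) per arm and gives 79.3, 78.2, 76.0 and 71.0%, which costs more once sharing is common.

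Room moves can still expose some controls, so the change reduces contamination without fully removing it.
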